5.0 Study Procedures

If the patient remains asymptomatic at rest (defined as no chest pain, shortness of breath, or dizziness), transfusion would be determined by randomization to the liberal transfusion strategy to maintain Hgb at 7 g/dL or the conservative transfusion strategy of 5.5 g/dL. After each unit of blood is transfused a Hgb level would be checked to ensure appropriate Hgb levels are maintained as well as routine clinical practice (typically daily Hgb levels drawn until at least 2 consecutive days show no further drop with no further procedures or bleeding expected). If the patient's Hgb does not drop below 7.0 g/dL, randomization will not be done but patient will still be followed and patient outcomes will be collected as part of a non-treatment group.

As noted in Section 4.0, a consensus group consisting of multiple physicians and the service chiefs from the Trauma Service (General Surgery), Orthopaedic Trauma Service, Anesthesia, and Physical Medicine and Rehab agreed to the following escape criteria to transfuse regardless of Hgb level or arm of randomization:

Escape Criteria

1. Patient has any of the following symptoms at rest: chest pain, shortness of breath, dizziness
2. Patient has a mean arterial pressure less than 50 mmHg that is not responsive to fluid resuscitation
3. At any time the patient's heart rate increases by more than 30% above baseline while under anesthesia
4. The patient's urine output drops to less than 0.5 mL/kg/hour and remains decreased despite adequate rehydration with fluids
5. Any objective evidence of cardiac ischemia including the following: EKG changes such as ST depression, an elevation of serum cardiac markers, a base deficit greater than 6, lactate greater than 2.5 that does not respond to fluid resuscitation
6. A decrease in systolic blood pressure by 10% or more with exercise (physical therapy) that does not improve with fluid resuscitation
7. Uncontrolled source of hemorrhage

In addition to being followed daily while inpatient, patients would be followed at routine intervals following injury: 2 weeks, 6 weeks, 3 months, 6 months, 9 months, and 1 year. Radiographic and clinical data will be collected specific to the patient's musculoskeletal injury and based on standard of care. The primary outcome is infection defined as superficial infection (cellulitis treated with oral antibiotics) or deep infection (requires IV antibiotics or surgical debridement), osteomyelitis, pneumonia, urinary tract infection.

Secondary outcomes include renal insufficiency, cardiac ischemia or myocardial infarction, deep venous thrombosis, or any other medical complication encountered in the patient's hospital or post-discharge course felt to be possibly related to the patient's injury, procedure, or as a result of transfusion. Secondary outcomes will also include standardized patient outcome scores; specifically, the Musculoskeletal Functional Assessment (MFA) done at baseline, 6 months, and 1 year, and the two minute walk test which would be conducted daily by a certified physical therapist while the patient is an inpatient and after they have been cleared for ambulation. Length of hospital stay will be recorded. Return to surgery or repeat hospitalization due to a complication will be other secondary outcomes. Completion of the Musculoskeletal Functional Assessment at 6 months and 1 year may be done via phone or mail, if the subject is unable or unwilling to return for clinic follow up.

Other possible risks, no matter which group subjects are randomized to, are:

- Infection
- Osteomyelitis
- Pneumonia
- Urinary tract infection
- Renal insufficiency
- Acute renal failure
- Cardiac ischemia or infarct
- Myocardial infarction
- Pancreatitis
- Deep venous thrombosis
- Pulmonary embolism
- Anoxic brain injury
- Death
- Delayed union
- Non-union
- Compartment syndrome
- Nerve palsy

Risk level is the same for all events listed. These risks are possible but there is a low chance for occurrence.

6.0 Reporting of Adverse Events or Unanticipated Problems involving Risk to Participants or Others

Any adverse event identified by a member of the care or research team from any participating site will be documented in writing and the lead site principal investigator will be notified of adverse events as they occur. All serious adverse events, protocol deviations, and noncompliance will be reported to the IRB in accordance with IU IRB policies and procedures. Significant adverse events that meet the policy criteria will be reported to the IRB as they occur. All other adverse events will be documented and reported to the IRB at time of continuing review.

A Data Safety Monitoring Plan (DSMP) will be in place to compare provisional outcomes prior to final enrollment. Per the DSMP, an orthopaedic surgeon not involved with the study will serve as the reviewer, looking at study data for obvious trends in higher complications in one study group. Monitoring of data that has been collected from all participating sites will be done every 6 months and findings will be submitted to the IRB at the time of continuing review. The data safety monitoring board will be comprised of: [name]-Independent Orthopaedic Surgeon, practices at Methodist (Board Chair), [name]-Anesthesiologist at Eskenazi, [name]-General Surgeon at Eskenazi, and [name]- Biostatistician at Methodist. [name]- Assistant Research Professor of Orthopaedic Surgery at IU will provide statistical analysis as needed. The DSMB has the independent ability to stop the study at any time if there is a concern for patient safety.

7.0 Study Withdrawal/Discontinuation

Subjects have the right to withdraw from the study at any time and for any reason without prejudice to future medical care. If a subject wishes to withdraw from the study, they must notify a member of the research team. Once withdrawn, no further data will be collected from the subject.

8.0 Statistical Considerations

Sample size:

This is a pilot study since the primary purpose of this study is to collect preliminary data on estimating the complication rates for orthopedic trauma patients who will receive blood transfusion either with a liberal transfusion strategy or a conservative strategy. The primary outcome of this study is whether a patient develops a complication while following a

conservative or liberal transfusion strategy for anemia. From our retrospective study, we anticipate the true complication rate would be anywhere between 30% and 50%. We want to estimate this proportion with 95% confidence and no more than 14% margin of error. With a sample size of 50 per group we would be able to reach this goal. For example, if the true proportion is 40%, the margin of error will be 13.6% and the maximum margin of error would be 13.9% when the true proportion is 50%.

Up to 370 subjects will be enrolled as part of the non-treatment group.

Data Analysis:

The primary endpoint is a dichotomous outcome, the presence or absence of a complication at post blood transfusion. A point estimate (sample proportion) and a 95% confidence interval for the proportion will be reported. This proportion will be computed for each of the two blood transfusion strategies. Although we did not power the study to detect a difference in complication rate between two strategies, we will compare the complication rates between two groups of patients. Descriptive statistics, like, mean, median, standard deviation for continuous outcomes will be used to describe the subjects' characteristics at baseline. Frequency counts and percent will be used for the categorical outcomes. Baseline clinical and demographic data will be compared between two groups to assess the effectiveness of the randomization. Dichotomous and ordinal variables will be examined using chi-square tests and continuous measures with Student's t-tests. Exploratory analysis will be performed to compute p-values which will be presented as an aid to evaluate the overall comparability of the treatment groups at baseline. Logistic regression model will be used to compare the complication rate or infection rate between two groups and baseline covariates will be included in the model if two groups are found to be significantly different in those covariates.

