2.0 Rationale and Specific Aims

Transfusion of Orthopaedic trauma patients is routinely done in asymptomatic individuals as there is no accepted national standard or recommendations from the American Academy of Orthopaedic Surgeons or the Orthopaedic Trauma Association for what level of anemia is appropriate in an asymptomatic patient. Individual practitioners typically make this decision based on anecdotal experiences and expert opinion. No prospective study has been performed to date to answer this question in this patient population.

The null hypothesis of this proposed pilot study is that no difference will be seen with a liberal transfusion strategy to keep a patient's hemoglobin above 7 g/dL versus a conservative strategy to keep the patient's hemoglobin above 5.5 g/dL in patients asymptomatic at rest. The primary outcome of this pilot study will be infection; defined as postoperative wound infection (superficial or deep) or other perioperative infection but not surgical site (urinary tract infection or pneumonia). Deep infection is defined as the need for intravenous antibiotics or a return to surgery for debridement. Superficial infection is defined as the use of oral antibiotics only successfully treat a surgical site infection. Secondary outcomes will include pulmonary embolism, deep venous thrombosis, acute renal failure or insufficiency, nonunion, delayed union, compartment syndrome, osteomyelitis, nerve palsy, anoxic brain injury, cardiac ischemia or infarct, pancreatitis, or death, and the musculoskeletal functional assessment. These same outcomes were evaluated in the retrospective study done at this institution which found no difference within any one complication, but when all complications were pooled there was a higher complication associated with the liberal transfusion strategy.

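### Sections 2.0 and 5.0 make infection the primary outcome, Section 8.0 makes it any complication and plans only for that, and the two infection definitions disagree

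*Combined protocol and SAP*

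**What the plan says.** **Section 2.0, Rationale and Specific Aims.** "The primary outcome of this pilot study will be infection; defined as postoperative wound infection (superficial or deep) or other perioperative infection". The non-wound part is described as "other perioperative infection but not surgical site (urinary tract infection or pneumonia". The rest of the list is secondary: "Secondary outcomes will include pulmonary embolism, deep venous thrombosis, acute renal failure or insufficiency, nonunion, delayed union, compartment syndrome, osteomyelitis, nerve palsy", followed by anoxic brain injury, cardiac events, pancreatitis, death and the functional score. The section adds that the institution's retrospective study looked at the same outcomes. That study found no difference for any single complication, but a higher rate with liberal transfusion once all were pooled.

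**Section 5.0, Study Procedures.** "The primary outcome is infection defined as superficial infection (cellulitis treated with oral antibiotics) or deep infection (requires IV antibiotics or surgical debridement), osteomyelitis", with pneumonia and urinary tract infection completing the list. Renal, cardiac and thrombotic events are secondary, along with "or any other medical complication encountered in the" patient's course that is felt to be possibly related to the injury, the procedure or transfusion.

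**Section 8.0, Statistical Considerations.** Under sample size: "The primary outcome of this study is whether a patient develops a complication while following a" given strategy. Under data analysis: "The primary endpoint is a dichotomous outcome, the presence or absence of a complication at post blood transfusion". The anticipated rate of 30% to 50%, the 14-point margin, and the proportion with 95% confidence interval for each strategy all refer to this outcome. Infection is named once, in the logistic regression sentence, as an alternative to the complication rate.

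**The concern.** Two sections and the statistical section name different primary outcomes, and the two are not synonyms. Under Section 8.0 a patient with only a deep venous thrombosis is a primary event; under Sections 2.0 and 5.0 that patient is not.

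The stated purpose of the pilot is to estimate a rate for later use. While the sections disagree, a later trial cannot tell which rate was pre-specified, and whichever endpoint looks more useful could be reported as the primary one. The choice is not neutral, because the retrospective study found its signal only after pooling all complications.

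Settling on infection would not be enough, since two people applying Sections 2.0 and 5.0 could classify the same patient differently.

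**Working it through.** **1. The planned precision, reproduced.** Inputs from Section 8.0: n = 50 per group, 95% confidence (z = 1.96), limit 14 points. The Wald half-width is 1.96 × √(p(1 − p)/50).

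- p = 0.40: 1.96 × √(0.24/50) = 13.58 points (plan: 13.6).
- p = 0.50: 1.96 × √(0.25/50) = 13.86 points (plan: 13.9).
- Inverse at p = 0.50: n = 1.96² × 0.25/0.14² = 49 (plan: 50).

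The arithmetic is right for the complication outcome.

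**2. The same formula for infection.** The documents give no infection rate, so the rates below are assumptions.

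| Assumed infection rate | Margin at n = 50 (points) |
|---|---|
| 10% | 8.3 |
| 15% | 9.9 |
| 20% | 11.1 |
| 25% | 12.0 |
| 30% | 12.7 |

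Because p(1 − p) is largest at 0.50, the margin cannot exceed 13.9 points, and 50 per group meets the 14-point limit for either outcome.

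**3. The definitions side by side.**

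| Item | Section 2.0 | Section 5.0 | Section 8.0 |
|---|---|---|---|
| Primary outcome | Infection | Infection | A complication |
| Osteomyelitis | Secondary | Part of primary | Not addressed |
| Superficial infection | Any surgical site infection managed with oral antibiotics alone | Cellulitis managed with oral antibiotics | Not addressed |
| Urinary tract infection, pneumonia | Primary, under the label perioperative | Primary, no such label | Not addressed |
| Thrombotic, renal, cardiac events | Secondary | Secondary | Not listed, but within a complication |
| Planning rate and 95% interval | None | None | Complications only |

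**4. What counts as a complication.** Section 2.0's infections plus its secondary clinical events form a finite list, and it matches the list searched in the retrospective study (Appendix K, Methods). Section 5.0 then reopens it with "or any other medical complication encountered in the" patient's course.

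**5. The window.** Section 5.0 schedules visits to 1 year, Section 10.0 refers to one-year follow-up, and the Appendix F intervals end at 1 year. None of these is attached to the primary outcome. The only timing given with it in Section 8.0 is after transfusion ("The primary endpoint is a dichotomous outcome, the presence or absence of a complication at post blood transfusion"). Randomization takes place when hemoglobin falls below 7 g/dL (Section 4.0). A patient assigned to the 5.5 g/dL strategy who stays above that level and meets no escape criterion (Section 5.0) is not transfused, so that wording gives the patient no starting point.

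**The case against.** The strongest reply is that little of practical weight turns on this. Infection is a subset of complications, so both proportions can be computed from the same forms. The sample size serves either outcome, and the plan says the between-group comparison was not powered. All of that stands. It does not say which proportion is the primary result, and estimating that proportion is what the pilot is for.

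Several stronger readings are tempting, and the documents do not support them.

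- A reader might infer that complications are nowhere listed for this trial. Section 2.0 does give a finite list; the defect is that Section 5.0 reopens it.
- A reader might infer that no assessment period was intended. One year is the evident intention; what is missing is the link to the primary outcome.
- A reader might treat perioperative in Section 2.0 as a firm time limit that conflicts with Section 5.0. It may only be a label separating these infections from wound infections. No perioperative period is defined, so the word needs clarifying.
- A reader might infer that never-transfused patients will be dropped. Section 8.0 also speaks of following a strategy and computes the proportion for each strategy, which points to grouping by strategy. The fault lies in the timing phrase.

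**Conclusion.** The contradiction is established by the text alone and should be resolved before any analysis. As written, Section 8.0 reports as primary an endpoint whose non-infectious parts Sections 2.0 and 5.0 call secondary. Infection, primary in those two sections, has no planning rate and no planned interval. The infection definitions conflict on osteomyelitis and on superficial infection, and are unclear on perioperative.

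A reader might also infer that 50 per group is wrong for infection, or that false-positive error is seriously inflated. Neither follows. The margin stays at or below 13.9 points at any rate. On error, take 50 per arm, no true difference, infections as a subset of complications, and an unadjusted logistic Wald test. Exact enumeration then gives a 5.4% to 9.0% chance that at least one of the two endpoints reaches p < 0.05, against 4.5% to 5.7% for complications alone. That assumes complication rates of 30% to 50%, with 25% to 75% of patients with a complication having an infection; the documents do not give this share. The effect is modest, and the conclusion does not depend on it.

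**What to change.** The sponsor chooses one primary outcome, infection or any complication; the documents contain support for each. Then:

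- State it identically in Sections 2.0, 5.0 and 8.0, with one closed component list. For complications, use the clinical events already in Section 2.0. The list must settle where osteomyelitis belongs, which definition of superficial infection applies, and whether perioperative is a time limit.
- Replace the after-transfusion wording with one window, for example from randomization to the 1-year follow-up already planned.
- Report the proportion and 95% confidence interval by randomized strategy for the primary outcome.
- Make the other endpoint a named secondary outcome with its own proportion, 95% confidence interval and the logistic regression already planned. The regression sentence then names a primary and a secondary outcome instead of two alternatives, and no planned analysis is lost.
- If infection is chosen, state its assumed rate and margin at n = 50, for example 8.3 points at an assumed 10% or 11.1 at 20%.

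The cost is wording in three sections and no additional patients. Appendix F already records an event date and has boxes for all five infection components in Section 5.0. No appended form shows a randomization date or a surgery date. Confirm that the first is captured elsewhere, and the second too if a perioperative limit is kept. If any complication is chosen, seven items on the Section 2.0 list now fall under Other on Appendix F and need boxes: pulmonary embolism, nonunion, delayed union, compartment syndrome, nerve palsy, anoxic brain injury and pancreatitis.

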4.0 Enrollment/Randomization

A consensus opinion was reached in a multidisciplinary manner with multiple members of the Trauma team (General Surgery), Anesthesia, Physical Medicine and Rehab, and the Orthopaedic Trauma Service. This team consisted of members from General Surgery ([name], [name], [name], [name]), Anesthesia ([name], [name], [name]), and Physical Medicine and Rehab ([name]) along with all members of the Orthopaedic Trauma Service ([name], [name], [name]) and the PI ([name]). The opinions in escape criteria and definitions will be referred to below as "consensus opinion". A biostatistician was consulted after he had reviewed the data from the retrospective study previously performed at this institution to help design an appropriately powered prospective randomized pilot study.

All Orthopaedic Trauma patients admitted to participating hospital will be screened for inclusion and exclusion criteria after they have been resuscitated and stabilized. The consensus opinion of the "stable" patient was defined as an awake and alert patient with normal urine output and systolic blood pressure greater than 90 mmHG for greater than 6 hours without fluid bolus or resuscitation. If a patient meets criteria for the study as noted above and is stable as defined above, the patient would be approached by either the Principal Investigator (PI) or a co-PI to determine interest and informed consent would be obtained for participation in the study. Patients who either refuse or are unable to consent will be tracked using the screening form. Enrollment would be performed in patients with a Hgb of 9 g/dL or less or in patients expected to drop below 9 g/dL with planned procedures or continued (controlled) bleeding. Randomization would not occur until the patient's Hgb dropped below 7 g/dL at which time a sealed envelope would be opened to determine if the patient would be randomized to a liberal transfusion strategy (transfuse to keep Hgb >7 g/dL) or a conservative strategy (transfuse to keep Hgb > 5.5 g/dL). If the patient's Hgb does not drop below 7.0 g/dL, randomization will not be done. Prior to starting enrollment, envelopes will be made by blinded personnel using a randomization list generated to assign subjects to receive treatment either after hemoglobin drops below 5.5 or after hemoglobin drops below 7.0. Randomization was

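### Section 8.0 words the primary endpoint in two incompatible ways, and the second ties it to a transfusion that some conservative-arm patients may never receive after randomization

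*Combined protocol and SAP*

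**What the plan says.** Section 8.0 describes the primary endpoint three times.

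- Sample size, purpose statement: the aim is "estimating the complication rates for orthopedic trauma patients who will receive blood transfusion either with a liberal transfusion strategy" or a conservative one. This presumes that patients in both strategies are given blood.
- Sample size, outcome: "The primary outcome of this study is whether a patient develops a complication while following a" conservative or liberal strategy. This depends on the strategy and not on receiving blood.
- Data Analysis: "The primary endpoint is a dichotomous outcome, the presence or absence of a complication at post blood transfusion". This is anchored to a transfusion, with no start point or window.

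The text around these sentences speaks in terms of arms: "This proportion will be computed for each of the two blood transfusion strategies", and "Baseline clinical and demographic data will be compared between two groups to assess the effectiveness of the randomization". The target is a 95% margin of at most 14 points with 50 per group, for rates expected to lie between 30% and 50%.

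Section 4.0 sets the moment of randomization: it waits until the patient's "Hgb dropped below 7 g/dL at which time a sealed envelope would be opened". Section 5.0 then says that in patients without symptoms at rest "transfusion would be determined by randomization to the liberal transfusion strategy to maintain Hgb at 7 g/dL or the conservative transfusion strategy" of 5.5 g/dL, and it lists escape criteria that permit transfusion in either arm. Section 5.0 times the follow-up visits from injury, out to 1 year, and Section 10.0 refers to one year of follow-up.

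**The concern.** The two endpoint wordings pick out different patients and different periods, and the design makes them diverge by arm. A liberal-arm patient is already below the transfusion threshold when the envelope is opened. A conservative-arm patient who stays above 5.5 g/dL and meets no escape criterion is not transfused under the protocol after randomization. For that patient the Data Analysis sentence supplies no period linked to the assigned strategy.

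An analyst who applied that sentence literally would have to score such patients as event-free or leave them out. The first lowers the conservative arm's rate if any of these patients has an event. The second shrinks that arm and compares groups no longer formed by randomization alone. In either arm, an event between randomization and the first transfusion would go uncounted.

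Estimating these rates is the stated purpose of the pilot, and Section 8.0 also compares the arms, including by logistic regression. The transfusion-anchored wording is not far-fetched: the retrospective study in Appendices J and K, from the same institution, divided patients by whether they were transfused. Section 8.0 names no analysis population and does not make randomization the start of the count.

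**Working it through.** **Step 1. Can a randomized patient go untransfused?** Entry to randomization is hemoglobin below 7 g/dL (Section 4.0). The liberal arm is transfused to stay above 7, so transfusion is due on assignment. The conservative arm is transfused to stay above 5.5, or on an escape criterion (Sections 4.0 and 5.0). A conservative-arm patient between 5.5 and 7 g/dL with no escape criterion gets no blood under the protocol. Such patients are possible by design; their number is not given.

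**Step 2. Does an earlier transfusion rescue the wording?** Section 3.0 requires more than 6 hours without bolus or transfusion before a patient counts as stable, so transfusion during resuscitation is allowed. A patient transfused then has a literal post-transfusion period, but one that began before assignment and has nothing to do with the strategy.

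**Step 3. Reproduce the plan's precision.** Inputs from Section 8.0: n = 50 per group, p from 30% to 50%, 95% confidence. Margin = 1.96 × √(p(1 − p)/n).

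- p = 0.40: 1.96 × √(0.24/50) = 13.58 points (stated 13.6%).
- p = 0.50: 1.96 × √(0.25/50) = 13.86 points (stated 13.9%).
- p = 0.30: 1.96 × √(0.21/50) = 12.70 points (not stated).

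The stated figures are reproduced, and they assume that all 50 patients per arm are evaluable.

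**Step 4. How many can be lost before the margin exceeds 14 points?**

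| True rate | Smallest n that meets 14 | Margin there | One fewer | Margin there | Lost from 50 when the target fails |
|---|---|---|---|---|---|
| 30% | 42 | 13.86 | 41 | 14.03 | 9 |
| 40% | 48 | 13.86 | 47 | 14.01 | 3 |
| 50% | 49 | 14.00 | 48 | 14.15 | 2 |

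This applies to any reason for being non-evaluable, including missing 1-year status. Section 7.0 stops data collection at withdrawal, and Appendix K reports 5 of 104 lost at one year, or 4.8%. If the same share were lost here (an assumption), that is 50 × 0.048 = 2.4 patients per arm.

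**Step 5. Can the distortion be sized?** Suppose a share f of the conservative arm is transfused after randomization, risk is the same with or without transfusion, and all events in transfused patients follow the transfusion. Scoring the others event-free would then lower the arm's rate by p(1 − f). The documents give no f. The equal-risk assumption also sits badly with Appendices J and K, which report higher complication risk with transfusion (p<0.01) and a dose effect (p=0.02). No percentage-point gap follows from the documents.

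**The case against.** The best reply is that the context already settles the meaning. One proportion is computed per strategy, the sample size is 50 per group, the baseline comparison is meant to check the randomization, and the other outcome sentence attaches the event to the strategy. The stated margins hold only if all 50 per arm count. On this view the Data Analysis sentence is loose phrasing. That is largely right as to intent, and under the by-arm reading there is no bias. It does not remove the conflict: the sentence that defines the primary endpoint for analysis states a different rule, and no other sentence overrides it.

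Three stronger readings are tempting and should not be drawn.

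- A reader might infer that the plan intends to drop untransfused patients or score them event-free. No section proposes either step.
- A reader might infer that untransfused conservative-arm patients have no post-transfusion period at all. Section 3.0 allows transfusion before enrollment, so some may have one, although it is unrelated to assignment.
- A reader might put a figure on the false difference between arms. That needs a transfused share the documents do not give and an equal-risk assumption that runs against the retrospective data.

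It is also fair to say that the same sentence needs rewriting for another reason: Sections 2.0 and 5.0 name infection as the primary outcome, while Section 8.0 names any complication. One edit can deal with both.

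**Conclusion.** The concern holds as a conflict in the wording of the primary endpoint, and it should be fixed. The Data Analysis sentence is wrong as written: taken literally, it conditions the endpoint on a post-randomization event whose frequency differs by arm by design. It is not evidence that a biased analysis is planned.

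The size of any distortion cannot be derived, and none is claimed. The one quantitative finding is that the precision target tolerates few non-evaluable patients: it fails at 3 lost of 50 for a 40% rate and at 2 of 50 for a 50% rate, though only at 9 of 50 for a 30% rate. These figures rest on the plan's own normal-approximation margin. The conclusion on wording rests only on the thresholds in Sections 4.0 and 5.0 and the text of Section 8.0.

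**What to change.** - **Sample size, purpose statement.** Replace the description of patients who are to be given blood under one or other strategy with *patients randomized to* a liberal or a conservative strategy.
- **Data Analysis, endpoint sentence.** Replace it with: *The primary endpoint is the occurrence or not of the primary-outcome event from randomization through the 1-year post-injury visit, in every randomized patient, analyzed by assigned arm, whether or not transfused.* This fixes the start of the count and says which 1-year point applies.
- **Missing status.** Add a sentence on how patients without 1-year status, including withdrawals, are counted. State that the 13.6% and 13.9% margins hold only with 50 evaluable patients per arm.
- **Randomization date.** Make it available to the analysis. None of the appended forms has a field for it; Appendix F already records the event date.
- **Which event.** In the same edit, reconcile infection (Sections 2.0 and 5.0) with any complication (Section 8.0). The endpoint sentence above leaves that choice open.

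The cost is a few sentences in Section 8.0 and one date in the analysis data. No patients or visits are added. Enrolling beyond 50 per arm to protect the margins against missing status would be a separate decision.
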